1.0 OBJECTIVES

1.1 Primary Objectives

1. To evaluate the safety of multiple combination regimens of IO-agents [PF04518600 (Ox40 agonist mAb), avelumab (PD-L1 antagonist mAb)], hypomethylator therapy (azacitidine), anti CD33 mAb (gemtuzumab ozogamycin, GO), Bcl-2 inhibitor (venetoclax) and smoothened pathway inhibitor (glasdegib) in patients with relapsed/refractory (RR) AML.

2. To evaluate the composite complete response (CRc) defined as CR + complete response with incomplete recovery of platelets (CRp) + complete response with incomplete recovery of counts (CRI) within 3 months of therapy initiation in patients with RR AML of:

Arm A. PF-04518600 alone,

Arm B. Azacitidine + venetoclax + GO

Arm C. Azacitidine + avelumab +GO

Arm D. Azacitidine + venetoclax + avelumab

Arm E. Azacitidine + avelumab + PF-04518600,

Arm F. GO + glasdegib

1.2 Secondary Objectives:

-To assess the morphologic leukemia free survival (MLFS), partial response (PR), hematologic improvement (HI) rate of patients with RR AML treated on arms A – F

-To assess relapse-free survival (RFS), time to next therapy (TNT), 4-week and 8-week mortality, and overall survival (OS) of patients with RR AML treated on arms A – F.

-To assess minimal residual disease (MRD) by multiparametric flow-cytometry at response (+/- 1 month) and assess correlation of MRD to OS in arms A – F.

1.3 Exploratory Objectives:

1. To study immunological and molecular features at baseline and at predefined time-points on-therapy with each combination in the peripheral blood and bone marrow to include: (a) quantification of immune ligand expression by the AML/MDS blasts and AML/MDS stromal components (MDSCs, monocytes and MSCs) including galectin 9, 4-1BBL, ICOSL, PD-L1, PD-L2, OX-40L, CD137L, others and (b) determination of the quantitative expression of positive and negative co-stimulatory molecules including 4-1BB, CTLA-4, ICOS, PD-1, OX40, LAG-3, TIM-3, HLA-DR, Ki67, others on T-lymphocyte subsets and (c) identification of the immunophenotype of tumor-infiltrating T-lymphocytes (TILs) pre- and post-therapy including CD8+, CD4+ effector, CD4+ regulatory TILs and central memory, effector memory, and naïve T-cell subsets among the CD4 and CD8 populations. These analysis will be done using multiparametric flow-cytometry (MFC) or multi-stain immunohistochemistry (IHC)

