5.4.8 Duration of Therapy

In the absence of treatment delays due to adverse events, treatment may continue until one of the following criteria applies:

1. Clinically significant progressive disease, or
2. Intercurrent illness that prevents further administration of either treatment agent, or
3. Patient request, or
4. General or specific changes in the patient's condition render the patient unacceptable for further treatment in the judgment of the investigator, or
5. Unacceptable toxicity that in the opinion of the investigator makes it unsafe to continue therapy.

It is planned that up to a total of 24 cycles of therapy will be administered for patients deriving benefit from this regimen. Continuation of therapy for patients completing 24 cycles of therapy may be considered on a case- by-case basis after discussion with the principal investigator and IND Office.

All patients receiving at least one dose of any of the two/three drugs to be received in the combination will be considered evaluable for toxicity and efficacy by intent-to-treat analysis.

5.5 Supportive Care:

Management Algorithms for Treatment of immuno-oncology agents Related

Adverse Events Immuno-oncology (I-O) agents are associated with AEs that can differ in severity and duration than AEs caused by other therapeutic classes. Avelumab and PF-04518600 are considered an immuno-oncology agent in this protocol. Early recognition and management of AEs associated with immuno-oncology agents may mitigate severe toxicity. These IO-agent/s has a known safety profile however, a general principle is that differential diagnoses should be diligently evaluated according to standard medical practice. Non- inflammatory etiologies should be considered and appropriately treated. Corticosteroids are a primary therapy for immuno-oncology drug-related adverse events, and avelumab is no exception. The oral equivalent of the recommended IV doses may be considered for ambulatory patients with low-grade toxicities. The lower bioavailability of oral corticosteroids should be taken into account when switching to the equivalent dose of oral corticosteroids. In cases with slightest suspicion of IO-toxicities it is encouraged that the treating physician consult the PI/Co-PI or immunotherapy expert in the department as soon as possible.

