8. Changes in drug dose and/or schedule must be discussed with and approved by the MDACC physician investigator, or they're representative prior to initiation, and will be documented in the patient record.

7.2.14 Patients with an objective response at completion of active study treatment will be followed for survival at MD Anderson Cancer Center (MDACC) every 3 to 6 months for up to 5 years after completion of active treatment and while still on study. If the patient is unable to return to MDACC the follow-up visits may be conducted via telephone.

Table 13. The study assessment schema is shown in tabular form below

Study Period/Cycle	Screening*	Treatment																		End of Study (EOS) ^{h,i}	Long-Term Follow-Up
		Cycle 1							Cycle 2							Cycle 3					
Cycle Day		1	8	14	15	22	28	1	8	14	15	22	28	1	8	14	15	22	1	30 Days After Last Dose	Every 3-6 months
Study Day	-14 to 0	1	8		15	22		29	36		43	50		57	64	70	71	78	—		
Complete history	X	X						X						X					X		
Physical examination ^a	X	X						X						X					X	X	
Vital Signs ^{**}		X		X				X		X				X		X			X		
Performance status	X	X						X						X					X	X	
Document all measurable disease (if present)	X																				
Concomitant medications ^a	X	X						X						X					X		X
Chest X-ray PA/Lateral	X																				
Nasal Wash PCR	X																				
ECHO/MUGA	X																		Q 3 cycles		
ECG ^k	X	X						X						X					X		
TropI, CK, CK-MB, BNP ^k	X							X						X					X		
CBC with differential ^b	X	X	X	X	X	X	X	X	X	X	X	X	X	X	X	X	X	X	X	X	

Sodium, Potassium, Chloride, glucose, uric acid, bicarbonate, BUN, Creatinine, total bilirubin, direct bilirubin, calcium, magnesium, ALT, or AST, alk phos ^b	X	X	X			X	X		X	X		X	X		X	X		X
Urinalysis	X	X						X				X				X		
Testosterone (males), GnRH	X																	
TSH, total T3, free T4, cortisol ^c	X	X						X				X				X		
Pregnancy test ^d	X																	
Bone marrow aspirate/biopsy ^e	X						X									X		
Correlative	Screening	Cycle 1					Cycle 2				Cycle 3				Subsequent cycles			EOS
Optional correlatives on blood ^f	X				Day 28				Day 28						Day 28 of cycles 2,4, 8, prog		If possible	
Optional correlatives on bone marrow ^g	X				Day 28				Day 28						Day 1 of cycle 2, 4, 8, prog		If possible	

* Samples collected at screening do not need to be repeated on Day 1 of Cycle 1.

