^gCorrelative studies will be collected on bone marrow at baseline, day 28 (+/- 4 days), then on day 28 (+/- 4 days) of cycles 4, 8and at progression if possible.

^hEOS visits include a physical examination, CBC with differential and platelets and a limited chemistry profile (total bilirubin, serum creatinine, SGPT or SGOT). A bone marrow aspiration may be done if non-response or progressive disease cannot be unequivocally diagnosed from peripheral blood.

ⁱSubject will be followed for toxicity for at least 30 days after the last protocol treatment. The 30-day follow-up visit (+ or – 5 days) will be scheduled as a clinic visits for clinical evaluation and physical examinations. If the patient cannot make it to the MDACC clinic for this visit, the required follow up treatment procedures may be done with a local physician and the records forwarded to MDACC. The research nurse will contact the patient by telephone and get a verbal assessment of the patient's condition. The phone conversation will then be documented in the patient's charts.

^j For patients that remain on study with no significant toxicity for more than 6 months, subsequent evaluations during study may be modified after discussion with the principal investigator. These include a decrease in frequency of bone marrow aspirations to every 6-12 months (or as clinically indicated), correlative studies to every 6-12 months (or suspension of sample collection for correlative studies), other laboratory tests to once every cycle.^k Perform at specified time-points and repeat as clinically indicated^L ECG on day 1 of every cycle of therapy

^k Only for patients on glasdegib-containing arm

Data regarding adverse events will be collected during the study. Protocol specific data will be entered into the electronic case report form (eCRF). AEs will be recorded in the Case Report Form (eCRF) as described under section 10.0.

Treatment may be discontinued for a variety of reasons, including patient withdrawal, investigator decision, and reasons specified by the protocol. Reasons for discontinuation of treatments are described in section 9.0.

8.0 CRITERIA FOR RESPONSE:

Response Criteria for AML

Responses will be assessed by the International Working Group for AML¹¹⁸. Responders are patients who obtain a CR, CRp, CRi, or PR, with or without cytogenetic response, hematologic improvements, and morphologic leukemia-free state.

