9.0 DISCONTINUATION OF TREATMENT

9.1 Discontinuation Criteria for Individual Patients

9.1.1 Patient Withdrawal

Patients may voluntarily withdraw consent to participate in the clinical study at any time and without giving any reason. Their withdrawal will not jeopardize their relationship with their healthcare providers or affect their future care. Patients may also choose to withdraw from study treatment, but agree to remain in the study for follow-up procedures.

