9.1.4 Follow-Up at Treatment Discontinuation or Early Withdrawal

Patients who discontinue treatment for any reason should complete end-of-treatment procedures when possible. End of treatment procedures will include a physical examination, CBC with differential and platelets and a limited chemistry profile (total bilirubin, serum creatinine, SGPT or SGOT). A bone marrow aspiration may be recommended only if non-response or progressive disease cannot be unequivocally diagnosed from peripheral blood. Although treatment will be discontinued at that time, all patients who do not withdraw consent for follow-up, die, or become lost to follow-up, will remain on study for follow-up evaluations. Subject will be followed for toxicity for at least 100 days after the last protocol treatment. The 100-day follow-up visit (+ or - 5 days) will be scheduled as a clinic visits for clinical evaluation and physical examinations. If the patient cannot make it to the MDACC clinic for this visit, the required follow up treatment procedures may be done with a local physician and the records forwarded to MDACC.

The research nurse will contact the patient by telephone and get a verbal assessment of the patient's condition. The phone conversation will then be documented in the patient's charts.

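### Scheduled survival follow-up names only patients in response at end of treatment, although OS is estimated in everyone dosed; read literally, this biases OS upward.

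*Combined protocol and SAP*

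**What the plan says.** Section 1.2 lists "4-week and 8-week mortality, and overall survival (OS) of patients with RR AML" among the secondary objectives, for patients treated on arms A to F. Section 11 plans Kaplan-Meier estimation of OS, log-rank tests between groups and a Cox model relating MRD to OS. Its efficacy set is everyone with at least one dose. It does not define the OS start date, event or censoring.

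Four places bear on who is followed, and for how long:

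- **Section 7.2.14:** "Patients with an objective response at completion of active study treatment will be followed for survival", every 3 to 6 months for up to 5 years, by telephone if the patient cannot return.
- **Section 9.1.4:** "all patients who do not withdraw consent for follow-up, die, or become lost to follow-up, will remain on study for follow-up evaluations". Its only timed contact is for safety: "Subject will be followed for toxicity for at least 100 days after the last protocol treatment".
- **Section 9.1.1:** "Patients may also choose to withdraw from study treatment, but agree to remain in the study for follow-up procedures". No schedule is attached.
- **Table 13:** a "Long-Term Follow-Up" column at 3 to 6 months, with no stated limit to responders and no visible survival-status row. Footnote i says the subject "will be followed for toxicity for at least 30 days after the last protocol treatment".

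**The concern.** The population followed for survival and the population analysed for survival do not match. Under the literal reading of 7.2.14, whether a patient is contacted after the last safety visit depends on response, and response predicts death. That is informative censoring. Kaplan-Meier assumes that censored patients have the same future as those who remain, so it would give the dropped non-responders the prognosis of responders.

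The wording also leaves out some responders. Section 5.4.8 says that "treatment may continue until one of the following criteria applies" and lists progressive disease first, so a patient who responds and then relapses on treatment is not in response at completion.

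The reported OS curves are at stake, and with them the log-rank comparisons and the MRD model, because arms or groups with different response rates would be censored to different degrees. Four- and eight-week mortality are less exposed: one 28-day cycle plus 30 days is 58 days, just past 8 weeks. The CRc endpoint and the futility and toxicity rules do not use OS.

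**Working it through.** The plan gives no OS sample size, event count or target, so there is no planned OS figure to reproduce. The check is an illustration of how large the bias could be.

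**Inputs from the documents.** Section 2.6.2 (azacitidine + nivolumab, 70 patients): 29 with response or stable disease, median OS 16.1 months; 41 without, median 4.1 months. Last timed contact after treatment: 30 days (Table 13, footnote i) or 100 days (Section 9.1.4). Cycle length: 28 days.

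**Assumptions.** Survival is exponential within each group. The 41/70 group receives 1, 2 or 3 cycles and is not contacted afterwards. The 29/70 group is fully followed.

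**Step 1, true curve** (t in months):

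S(t) = (29/70)·exp(−ln2·t/16.1) + (41/70)·exp(−ln2·t/4.1)

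S(12) = 0.247 + 0.077 = 0.324, and S(t) = 0.5 at t = 6.7 months.

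**Step 2, curve under literal follow-up.** Non-responders are censored at c = (28 × cycles + 30 or 100)/30.44. In large samples Kaplan-Meier then estimates S(t) up to c, and S(c)·exp(−ln2·(t − c)/16.1) after c.

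Example, one cycle and 30 days: c = 58/30.44 = 1.91; S(c) = 0.806; at 12 months 0.806 × exp(−ln2 × 10.09/16.1) = 0.522.

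| Last contact | Cycles | c (months) | Non-responders alive at c | KM median (months) | KM 12-month OS |
|---|---|---|---|---|---|
| 30 days | 1 | 1.91 | 72% | 13.0 | 52.2% |
| 30 days | 2 | 2.83 | 62% | 11.6 | 49.2% |
| 30 days | 3 | 3.75 | 53% | 10.3 | 46.5% |
| 100 days | 1 | 4.20 | 49% | 9.7 | 45.3% |
| 100 days | 2 | 5.12 | 42% | 8.5 | 43.0% |
| 100 days | 3 | 6.04 | 36% | 7.4 | 41.0% |
| True | | | | 6.7 | 32.4% |

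**Step 3, partial tracing.** If a fraction q of non-responders is fully followed, Kaplan-Meier after c is S(c)·G(t)/G(c), where G is S with the second weight multiplied by q.

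- q = 0.5: median 6.8 to 8.0 months, 12-month OS 35.7% to 38.8%.
- q = 0.9: median 6.7 to 6.9 months, 12-month OS about 33%.
- q = 1: the true curve.

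**Step 4, sensitivity to the responder share.** With shares of 30% and 45%, the historical and target CRc rates in Section 11, true 12-month OS is 27% and 34%. Under literal follow-up, 12-month OS is overstated by about 8 to 24 percentage points and the median by 0 to 6.6 months. The median bias is zero only when c falls after the true median.

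**Step 5, arm-sized samples.** Simulation with n = 24 and n = 30, the 29/70 share and 1 to 3 cycles mixed gives a mean 12-month estimate of 48% to 49% (30-day contact) or 43% (100-day contact), against a true 32%.

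**The case against.** The best counter-argument is that the sections complement each other. Section 7.2.14 does not say that only responders are followed. Section 9.1.4 covers patients who discontinue, which is where most non-responders fall; its only exits are withdrawal of consent, death and loss to follow-up, and its 100 days is a minimum for toxicity. Table 13 supplies the same 3 to 6 month interval without a responder limit. On that reading everyone is followed and only wording is missing. The same centre also reported survival for its 41 non-responders in the earlier trial, so zero tracing is an unlikely case.

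Much of this stands, and it is why the bias is conditional. It does not remove the problem: under 9.1.4 a non-responder has no survival interval, duration or data item, and the only sentence that provides them names a different group.

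The inputs are soft. In the source trial, 13 of the 29 better-prognosis patients (7 with haematologic improvement, 6 with stable disease) were counted because they stayed on study beyond 6 months, whereas the exponential model has 23% of that group dead by then. Letting 13/29 survive to 6 months with certainty, one common hazard otherwise and the group median kept at 16.1, moves the true median to 7.3 months and true 12-month OS to 33%. The literal reading then gives 8.3 to 13.3 months and 41% to 54%, so the conclusion is unchanged.

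Precision is also low. At n = 24 the 95% half-width for 12-month OS is about 1.96 × √(0.324 × 0.676/24) = 19 points, more than the 9 to 13 point bias in the 100-day case. Bias adds to that uncertainty, however, and does not average out. Finally, censoring at last known alive is the usual convention, so the missing sentence alone biases nothing.

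**Conclusion.** The concern holds and should be fixed. The inconsistency between Sections 7.2.14, 9.1.4 and Table 13, and the absence of an OS censoring rule, are plain from the text. The upward bias depends on 7.2.14 being followed literally. In that case the illustration gives a median 0.7 to 6.3 months too high (7.4 − 6.7 to 13.0 − 6.7) and a 12-month OS about 9 to 20 points too high (41.0 − 32.4 to 52.2 − 32.4). Both shrink as more non-responders are traced and vanish if all are.

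These sizes rest on exponential survival, medians borrowed from another trial, a better-prognosis group that includes stable disease, an assumed 1 to 3 cycles of treatment, and 30 or 100 days taken as the last contact although both are stated minimums. Relapsed responders are not modelled. The direction is more secure than the size. For scale, Section 2.6.2 reports a favourable comparison with historical controls on medians of 6.0 and 4.7 months, a difference of 1.3 months; most of the illustrated range exceeds that.

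**What to change.** - **Section 7.2.14:** replace the population with all patients who received at least one dose, followed for survival and next anti-leukemic therapy at the existing 3 to 6 month interval for up to 5 years or until death, regardless of response, with telephone or record review accepted.
- **Section 9.1.4 and Table 13:** refer to that schedule, and add a survival-status row to the long-term column. Reconcile the 30-day and 100-day toxicity visits.
- **Section 11:** define OS as time from a stated start date to death from any cause, with patients not known to have died censored at the date last known alive.

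The cost is a few sentences and a table row, plus some calls or chart checks. Under the assumptions above, non-responders alive at last contact number about 24 × 41/70 × (0.36 to 0.72), or 5 to 10, in a 24-patient arm, and 30 × 41/70 × (0.36 to 0.72), or 6 to 13, in the 30-patient arm. Telephone follow-up is already allowed. If staff already track everyone, the amendment only records current practice.

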9.0 DISCONTINUATION OF TREATMENT

9.1 Discontinuation Criteria for Individual Patients

9.1.1 Patient Withdrawal

Patients may voluntarily withdraw consent to participate in the clinical study at any time and without giving any reason. Their withdrawal will not jeopardize their relationship with their healthcare providers or affect their future care. Patients may also choose to withdraw from study treatment, but agree to remain in the study for follow-up procedures.

9.1.2 Investigator Discontinuation of Patient

The investigator may exercise medical judgment to discontinue study treatment if clinically significant changes in clinical status or laboratory values are noted.

9.1.3 Criteria for Protocol-Defined Required Discontinuation of Treatment

The protocol requires discontinuation of study treatment for the following reasons:

1. Patient requests discontinuation.
2. Unacceptable toxicity that in the opinion of the investigator makes it unsafe to continue therapy.
3. Clinically significant progressive disease.
4. Investigator discretion.

9.1.4 Follow-Up at Treatment Discontinuation or Early Withdrawal

Patients who discontinue treatment for any reason should complete end-of-treatment procedures when possible. End of treatment procedures will include a physical examination, CBC with differential and platelets and a limited chemistry profile (total bilirubin, serum creatinine, SGPT or SGOT). A bone marrow aspiration may be recommended only if non-response or progressive disease cannot be unequivocally diagnosed from peripheral blood. Although treatment will be discontinued at that time, all patients who do not withdraw consent for follow-up, die, or become lost to follow-up, will remain on study for follow-up evaluations. Subject will be followed for toxicity for at least 100 days after the last protocol treatment. The 100-day follow-up visit (+ or - 5 days) will be scheduled as a clinic visits for clinical evaluation and physical examinations. If the patient cannot make it to the MDACC clinic for this visit, the required follow up treatment procedures may be done with a local physician and the records forwarded to MDACC.

The research nurse will contact the patient by telephone and get a verbal assessment of the patient's condition. The phone conversation will then be documented in the patient's charts.

9.2 Study Stopping Rules

The principal investigator and MDACC IND office have the right to terminate this clinical study at any time. The principal investigator and MDACC IND office, as appropriate, will be involved in any decisions regarding terminating the study, temporarily suspending enrollment, or stopping ongoing treatment with study treatment.

Reasons for terminating the clinical study or a study site's participation include, but are not limited to, the following:

- The incidence or severity of an adverse reaction related to treatment in this study or other studies indicates a potential health hazard to patients
- Data recording is significantly inaccurate or incomplete
- Study site personnel are noncompliant with study procedures
- Pattern of noncompliance is observed

9.3 Protocol Violations and Deviations

Protocol violations are defined as significant departures from protocol-required processes or procedures that affect patient safety or benefit potential, or confound assessments of safety or clinical activity. A protocol deviation is a departure from the protocol that does not meet the above criteria. Protocol violations or deviations may be grouped into the following classes:

- Enrollment criteria
- Study activities (missed evaluations or visits) except for those allowed per protocol

- Noncompliance with dose or schedule, including dose calculation, administration, interruption, reduction, or delay; or discontinuation criteria
- Investigational product handling, including storage and accountability
- Informed consent and ethical issues

